8.2. Efficacy Variables

Primary Efficacy Parameters:

- i. The proportion of subjects with symptomatic laboratory-confirmed COVID-19 identified after start of treatment and before the end of the 6-week treatment period
- ii. The proportion of subjects with symptomatic laboratory-confirmed VRI identified after start of treatment and before the end of the 6-week treatment period

Secondary Efficacy Parameters:

- i. The proportion of subjects hospitalized due to COVID-19 or complications thereof
- ii. Mortality due to COVID-19 or complications thereof

iii. The proportion of subjects (with or without symptoms) testing positive for antibodies to SARS-CoV-2 at either of the Week 6 or Week 8 visits

Exploratory Efficacy Parameters:	Hospitalization due to VRI or complications thereof, mortality due to VRI or complications thereof, proportions of subjects experiencing acute respiratory illness (ARI), hospitalization due to ARI or complications thereof, and mortality due to ARI or complications thereof.
----------------------------------	---

8.3. Response Definitions

ARI:	≥ 0.5 increase from baseline in mean symptom score for the chest/respiratory FLU-PRO domain or ≥ 0.5 increase from baseline in mean symptom score for at least two of the following FLU-PRO [®] domains: body/systemic, nose, throat.
COVID-19:	ARI after start of treatment and before the end of the 6-week treatment period associated with detection of SARS-CoV-2 by RT-PCR assay of nasopharyngeal swab.
VRI:	ARI after start of treatment and before the end of the 6-week treatment period associated with detection of any respiratory virus by RT-PCR assay of nasopharyngeal swab.

8.4. Statistical Methodology

The statistical methodology is described briefly below and will be described in detail in the Statistical Analysis Plan.

8.4.1. Efficacy Analyses

Efficacy analyses will be based on a population consisting of all subjects randomized without a laboratory-detected viral respiratory infection at the baseline visit (intention-to-treat or ITT population).

There will be two primary efficacy analyses:

- The proportion of subjects experiencing COVID-19 in the NTZ treatment group will be compared to that of the placebo treatment group using a two-sided Cochran-Mantel-Haenszel (CMH) chi-square test ($\alpha = 0.049$).
- The proportion of subjects experiencing VRI in the NTZ treatment group will be compared to that of the placebo treatment group using a two-sided CMH chi-square test ($\alpha = 0.001$).

Secondary analyses will be performed as follows:

- Proportions of subjects experiencing hospitalization due to COVID-19 or complications thereof will be compared by treatment group using a two-sided CMH Chi-square test (unadjusted $\alpha = 0.05$).
- Proportions of subjects experiencing mortality due to COVID-19 or complications thereof will be compared by treatment group using a two-sided CMH Chi-square test (unadjusted $\alpha = 0.05$).
- Proportions of subjects (with or without symptoms) testing positive for antibodies to SARS-CoV-2 at either of the Week 6 or Week 8 visits will be compared by treatment group using a two-sided CMH Chi-square test (unadjusted $\alpha = 0.05$).

Exploratory analyses will be performed as follows:

- Proportions of subjects experiencing each of the following will be compared by treatment group using a two-sided CMH Chi-square test (unadjusted $\alpha = 0.05$): (i) hospitalization due to VRI or complications thereof; (ii) mortality due to VRI or complications thereof, (iii) acute respiratory illness (ARI), (vi) hospitalization due to ARI or complications thereof; and (v) mortality due to ARI or complications thereof.

Other analyses may be performed as outlined in the study Statistical Analysis Plan.

8.4.2. Population Pharmacokinetics Analysis

On Week 3 and 6, the plasma samples will be collected before the morning dose (at the trough). These data will allow for analysis of relationships between trough plasma concentrations and clinical and virologic response.

Trough plasma concentrations of tizoxanide and tizoxanide glucuronide will be summarized descriptively for each of the treatment groups. Exploratory analyses will be conducted to evaluate the relationships between plasma concentrations and age, race, gender, body weight, body mass index, VRI and adverse events.

8.4.3. Safety Analyses

All randomized subjects who receive the study medication will be evaluated for drug safety. Safety analyses will be done descriptively.

9. INVESTIGATIONAL PRODUCTS

9.1. Drug Regimens, Administration and Duration

Group 1 (NTZ): Subjects will receive two NTZ 300 mg tablets b.i.d. with food (< 1 hour after food intake) and a B complex vitamin (██████████) b.i.d. for 6 weeks.

Group 2 (Placebo): Subjects will receive two placebo tablets b.i.d. with food (< 1 hour after food intake) and a B complex vitamin (██████████) b.i.d. for 6 weeks.

The food prior to drug intake should preferably be a high-fat meal, but at minimum a cereal bar.

All subjects will receive a vitamin B complex supplement one tablet twice a day (manufacturer's labeled dosing) to help mask any potential chromaturia attributed to NTZ and aid in maintaining study blinding.

9.2. Identity of Investigational Products

The active formulation for this study is a yellow, film-coated tablet that contains 300 mg NTZ plus standard excipients. The placebo tablet will have the same appearance and inactive ingredients as the active tablet.

The vitamin B complex supplement is [REDACTED] manufactured by [REDACTED] [REDACTED]. The supplement will supply each subject with the following Percent Daily Values based on a 2,000-calorie diet: vitamin B1 1,333%, vitamin B2 824%, vitamin B3 240%, vitamin B5 360%, vitamin B6 1000%, vitamin B7 100%, vitamin B12 15,000%, folate 100%, and vitamin C 267%.

[figure not shown]
9.3. Packaging and Labeling

NTZ or placebo tablets will be packaged in white 30 cc HDPE bottles, each containing 20 tablets. Each subject will receive a boxed kit containing 180 tablets (9 bottles). The subjects will take two tablets with food at each dosing time point. The kits will be stored at room temperature and will bear labels with the following information:

Table 6: Study Medication Labels

External Box Label	Principal Investigator:	
9 Bottles (20 Tablets Each)		
180 Tablets Total	Study N° RM08-3006	Treatment N°: XXXX
Lot:		
Take 2 Tablets by Mouth with Food Twice Daily		
Caution: New Drug-Limited by Federal Law to Investigational Use		
STORE AT ROOM TEMPERATURE • DO NOT USE BEYOND END OF STUDY		
KEEP OUT OF REACH OF CHILDREN		
Study Sponsor: The Romark Institute for Medical Research		
[REDACTED]		

Individual Bottle Label

9.4. Drug Accountability

Medication will be dispensed at baseline. Medication compliance will be reviewed with each subject at each scheduled and unscheduled visit, subjects will be asked to return the bottles in which the medication was dispensed along with any unused medication.

The Investigator or designee is required to maintain adequate records of the disposition of all study drug, including dates, quantity and use by subject. Unused supplies must be returned to the Sponsor.

9.5. Subject Compliance

Subject compliance with the protocol will be checked by the Investigator and recorded in the EDC system at each visit.

Subjects will be considered non-compliant if they have missed more than 20% of the doses of the study medication (major protocol violation). Non-compliance will not be cause for discontinuation of subject participation in the study.

9.6. Disallowed Medication

During the active treatment course of the study, concomitant use of medications considered major CYP2C8 substrates are prohibited, see below.

Table 7: Major CYP2C8 Substrates

Generic Name	Brand Name(s)	Therapeutic Use and/or Drug Class
Amodiaquine	BASOQUIN, CAMOQUIN, FLAVOQUIN	Antimalarial
Daprodustat (GSK1278863)	*	Antianemic, prolyl hydroxylase inhibitor
Dasabuvir (ABT-333)	EXVIERA	Antiviral, NSB5 inhibitor
Enzalutamide	XTANDI	Anticancer, antiandrogen
Montelukast	SINGULAIR	Antiasthmatic, LTRA
Pioglitazone	ACTOS	Antidiabetic, PPAR- γ agonist
Repaglinide	NOVONORM, PRANDIN	Antidiabetic, meglitinide analog

Source: [Backman et al. 2016](#).

*Currently listed as investigational only and not yet granted a trade name by the manufacturer.

Subjects are also prohibited from taking hydroxychloroquine, chloroquine, NTZ (except as the blinded investigational medication) or any other investigational medication or vaccine during the study. Since tizoxanide is highly protein-bound and may compete with plasma protein binding sites, co-administration of NTZ and warfarin should be avoided if reasonably possible. If co-administration of NTZ and warfarin cannot be avoided, the investigator must monitor prothrombin time and international normalized ratio (PT/INR) in subjects taking warfarin as clinically warranted.

Medications for pre-existing conditions that are not excluded (see exclusion criteria) should be continued as prescribed. The use of such medication will be recorded in the EDC system.

10. ADVERSE EVENTS

The term “adverse event” is defined for purposes of this study as any unwanted physical, psychological or behavioral change experienced by a subject during the course of the study and after taking the first dose of study medication regardless of its severity or relation to the study. Adverse events may include symptoms, signs, unexpected worsening of pre-existing conditions, clinically significant changes in laboratory values, diseases and syndromes, and significant and unexpected failures of pharmacological action of other medications. Symptoms of VRIs (cough, sore throat, nasal obstruction, fatigue, headache, myalgia, feverishness) and complications of VRIs will not be reported as adverse events.

Adverse events will be recorded on the appropriate EDC forms throughout the study, and the severity of each adverse event will be graded on a four-point scale: mild, moderate, severe, or life-threatening (See [Appendix II](#)). The duration of the adverse event and relationship to the study drug will also be recorded. All adverse events must be followed until their resolution or stabilization even beyond the planned study period.

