Overall, the type and severity of AEs reported in this population were similar to the total population and the known adverse event profile for the drug. In the pharmacokinetic study only two adverse events were reported in two subjects (headache and diarrhea), both were mild in nature and not considered to be related to nitazoxanide. In Phase 2b/3 and Phase 3 clinical trials, two subjects experienced serious adverse events unrelated to study medication, but rather related to a pre-existing history of a concurrent condition. One of the subjects experienced an exacerbation of congestive heart failure was hospitalized and subsequently recovered. The other subject had a history of severe back and neck pain and was hospitalized for musculoskeletal pain. This subject also recovered. The other adverse events experienced by geriatric subjects were mild to moderate in nature. The most commonly reported AEs (at least 2%) for geriatric subjects receiving nitazoxanide in Phase 3 studies (n = 75) regardless of causality assessment were: diarrhea (9.3%), chromaturia (6.7%), nausea (2.7%), and headache (2.7%). The rates of occurrence of AEs did not differ significantly from those of the placebo.

Population pharmacokinetic data for tizoxanide and tizoxanide glucuronide troughs (prior to next dose) from geriatric subjects receiving nitazoxanide 600 mg twice daily for 5 days is available for 50 subjects enrolled Phase 2b/3 and Phase 3 clinical trials. A comparison of this data to the adult population (18 to 64 years of age) from these studies is presented in the following table (NTZ 300 mg Tablets Investigators Brochure).

Table 4: Population Pharmacokinetics, Trough Data, for Geriatric Subjects ≥ 65 Years of Age from Phase 2b/3 and Phase 3 Clinical Trials

Metabolite	Trough Data Subjects ≥ 65 years	Trough Data Subjects 18 to 64 years
Tizoxanide	0.86 $\mu\text{g}/\text{mL}$ (n = 50)	0.81 $\mu\text{g}/\text{mL}$ (n = 1305)
Tizoxanide glucuronide	3.08 $\mu\text{g}/\text{mL}$ (n = 50)	2.34 $\mu\text{g}/\text{mL}$ (n = 1314)

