5.5. Week 1, Week 3, and Week 6 Evaluations (± 2 days)

A study physician, nurse or other study personnel will visit each subject at Week 1, Week 3, and Week 6, and the following procedures will be performed:

1. Physical examination as warranted by the Investigator for any change from baseline.
2. Body weight and collection of vital signs to include blood pressure, pulse, respiratory rate and body temperature.
3. Week 3 and Week 6 only, collection of blood sample for laboratory safety tests, pharmacokinetics (pre-dose) and anti-SARs-CoV-2 antibodies (antibody testing at Week 6 visit only).
4. Week 3 and Week 6 only, collection of urine sample for routine urinalysis.
5. Review of compliance with study medication, collection of medication bottle with any unused medications (Week 6 visit only), and completion of the pill count log form.
6. Review and recording of concomitant medications.
7. Review and recording of adverse events/side effects and complications. Note that all adverse events and complications must be followed until their resolution or stabilization even beyond the 8-week study period.

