10.1. Definitions

The following definitions will apply to the reporting of adverse events:

1. Serious Adverse Event: Any adverse experience occurring at any dose that is fatal or life threatening; requires in-patient hospitalization or prolongation of an existing hospitalization; is a persistent significant disability/incapacity; is a congenital anomaly or birth defect; or is an important medical event that may not result in death, be life-threatening, or require hospitalization but, based upon appropriate medical judgment, may jeopardize the subject and may require medical or surgical intervention to prevent one of the outcomes listed above.
2. Unexpected Adverse Event: Any adverse experience that is not identified in nature, severity, or frequency in the Investigator's Brochure for NTZ.
3. Severity of adverse events will be assessed by the Investigator using the Toxicity Grading Scale Tables provided in [Appendix II](#) (derived and adapted from “Guidance for Industry: Toxicity Grading Scale for Healthy Adult and Adolescent Volunteers Enrolled in Preventive Vaccine Clinical Trials”, US Dept. of HHS, FDA, CDER, September 2007 and the National Institutes of Health, National Cancer Institute Common Terminology Criteria for Adverse Events (CTCAE) version 5.0).

4. Causality (relationship to treatment) will be assessed as follows:

- *Definitely Related*: The adverse event is clearly related to the investigational agent(s) or research intervention: the adverse event has a temporal relationship to the administration of the investigational agent(s) or research intervention, follows a known pattern of response, and no alternative cause is present.
- *Probably Related*: The adverse event is likely related to the investigational agent(s) or intervention: the adverse event has a temporal relationship to the administration of the investigational agent(s) or research intervention, follows a known or suspected pattern of response, but an alternative cause may be present.
- *Possibly Related*: There is a reasonable possibility that the event may have been caused by or is linked in a significant way to the research; the adverse event has a temporal relationship to the administration of the investigational agent(s) or research intervention, follows a suspected pattern of response, but an alternative cause is present.

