10.2. Clinical Adverse Events

At the time of each return visit, the subject will be questioned regarding the occurrence and nature of any adverse events. All events must be recorded in the subjects' medical records and in the EDC system. Any subject affected will be examined by the Investigator as deemed necessary to ascertain the course of the event and any residual effects.

All moderate and severe adverse events will be reviewed by the Principal Investigator who will determine using his/her best clinical judgment whether they warrant the subject to be discontinued from the study. The Sponsor will be notified immediately if a subject is discontinued from the study. For all adverse events that require the subject to be discontinued from the study, relevant clinical assessments and laboratory tests will be repeated as clinically indicated until final resolution or stabilization of the event(s).

All subjects will be instructed to contact the Investigator, Investigator's assistants, or clinical personnel should the subject have any serious adverse experiences. Serious adverse events, including death regardless of the cause, must be reported to the Sponsor immediately (within 24 hours of the initial report).

A serious event requiring immediate notification by telephone is an event that:

- results in death
- is life threatening

- requires inpatient hospitalization or prolongation of an existing hospitalization
- is a persistent or significant disability/incapacity
- is a congenital anomaly/birth defect
- an important medical event that may not result in death, be life-threatening, or require hospitalization but, based upon appropriate medical judgment, may jeopardize the subject and may require medical or surgical intervention to prevent one of the outcomes listed above.

An overdose is defined as any intentional or unintentional consumption of the drug by any route that exceeds the highest dose stated in the Investigator's Brochure or in an investigational protocol, whichever dose is larger. Overdoses without an associated adverse event should be recorded, but not reported as an adverse event.

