### 2.2 Analysis Populations

#### 2.2.1 Population Definitions

Subjects will be considered enrolled in the study upon completion of the baseline procedures. The following analysis populations will be used in the study.

- **Safety Population** – the safety population includes all patients who are enrolled in the study and that have received at least one dose of the assigned treatment arm (NTZ or placebo)
- **Intention to Treat Population (ITT)** – the ITT population includes all patients in the safety population who did not have a laboratory detected respiratory virus infection at the baseline visit.

The safety population will be used for all safety analyses. The ITT population will be the primary population for all efficacy analyses.

Data listings displaying the patients excluded from each population will be created. These listings will be relative to all patients enrolled in the study.

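### Protocol 10 exempts VRI complications from adverse event reporting while 10.1 and 10.2 exempt nothing; if Section 10 is followed, VRI hospitalisations of subjects virus-positive at baseline are compared by arm in no table

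*Protocol*

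**What the plan says.** Protocol Section 10 starts from a wide definition of an adverse event: "any unwanted physical, psychological or behavioral change experienced by a subject during the course of the study", after the first dose and whatever its severity or cause. It then takes a class of events out: "Symptoms of VRIs (cough, sore throat, nasal obstruction, fatigue, headache, myalgia, feverishness) and complications of VRIs will not be reported as adverse events". Nothing there treats serious complications differently.

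Protocol 10.1 defines a serious adverse event as "Any adverse experience occurring at any dose that is fatal or life threatening; requires in-patient hospitalization or prolongation of an existing hospitalization", among other criteria. Protocol 10.2 adds: "Serious adverse events, including death regardless of the cause, must be reported to the Sponsor immediately (within 24 hours of the initial report"). Neither section mentions VRI.

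The SAP builds its adverse event and serious adverse event tables from reported adverse events in the safety population (SAP 5.2). The ITT population is the part of the safety population "who did not have a laboratory detected respiratory virus infection at the baseline visit" (SAP 2.2.1). The three hospitalisation tables in SAP 8.0, for COVID-19 (14.2.2.1), VRI (14.2.3.1) and ARI (14.2.3.4), are all ITT tables.

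**The concern.** Take a subject admitted to hospital with a complication of a laboratory-confirmed respiratory infection. Section 10 says that this is not reported as an adverse event. Sections 10.1 and 10.2 say that an event needing admission is serious and goes to the sponsor within 24 hours. Sites may resolve this differently, so the serious adverse event table would mean different things at different facilities.

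The second issue is where the data go if Section 10 prevails. Endpoint illness is often kept out of adverse event tables because the efficacy tables compare it. Here those tables leave out subjects who carried a virus at the first dose. The protocol makes such subjects likely. A COVID-19 case in the facility within the previous 10 days is an entry condition (4.1). The swab, randomisation and first dose all take place at the Day 1 visit, with no step that waits for the result (5.2). These subjects are exposed to study drug while already infected, so a difference between arms in their respiratory hospitalisations would be a safety finding. No planned table would show it.

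**Working it through.** **1. The rules side by side.** Section 10 removes VRI complications at any severity. Section 10.1 includes any fatal or hospitalised adverse experience. Section 10.2 includes death whatever the cause. For a fatal VRI complication the conflict is explicit. For a hospitalised one, it depends on whether the term used in 10.1 is meant to be narrower because of Section 10, which the protocol does not say.

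**2. Does the exclusion reach baseline-positive subjects?** Protocol 8.3 defines VRI as an ARI that arises after the start of treatment and before the end of the 6 weeks, with a virus detected by RT-PCR. It does not require the infection to be new. A baseline-positive subject who falls ill on treatment and has a positive swab therefore meets it.

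**3. Where a VRI hospitalisation would appear.**

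| Output | Population | If Section 10 is followed | If 10.1 and 10.2 are followed |
|---|---|---|---|
| Table 14.3.1.5, serious adverse events by arm | Safety | Absent | Present |
| Tables 14.2.2.1, 14.2.3.1, 14.2.3.4, hospitalisation by arm | ITT | ITT subjects only | ITT subjects only |
| Listing 16.2.6.2, by subject | Safety | Listed, not compared | Listed, not compared |
| All-cause deaths by arm (SAP 6.3) | Safety | Only if fatal | Only if fatal |

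All 3 hospitalisation tables are ITT only. Under Section 10, a non-fatal VRI hospitalisation in a baseline-positive subject reaches 0 between-arm tables.

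**4. Monitoring.** The first IDMC review looks at adverse event, vital sign and laboratory data (SAP 2.4). The stopping rule in Protocol 11.1 counts subjects with Grade 3 or 4 adverse events judged at least possibly related. An event never entered as an adverse event cannot contribute to the first of these data sources or be judged for the second.

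**5. Size.** Inputs: 400 subjects per arm; placebo rates of 5% for COVID-19 and 10% for VRI; an 80% reduction on NTZ (Protocol 8.1), hence 1% and 2%.

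- The plan's own figure first: expected COVID-19 events = 400 × 0.05 + 400 × 0.01 = 20 + 4 = 24, as in SAP 2.4.
- Expected subjects with a VRI = 400 × 0.10 + 400 × 0.02 = 40 + 8 = 48, COVID-19 included. Complications of these illnesses are what Section 10 keeps out of the adverse event tables.
- Baseline-positive subjects: the documents give no rate. Assuming 1% to 10%: 800 × 0.01 = 8 to 800 × 0.10 = 80. This is the number of subjects without a comparative table, not a number of hospitalisations.

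**6. The symptom list.** Section 10 names headache, fatigue and myalgia as VRI symptoms but does not point to the definition in 8.3. Appendix II grades the same three as adverse events. None of them alone triggers a Suspected ARI visit (Protocol 5.3), so often no swab will exist to settle the attribution.

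**The case against.** The best defence is that endpoint illness is deliberately kept out of the adverse event tables, and that a serious adverse event is by nature a subset of adverse events, so Section 10 governs and there is no contradiction. For ITT subjects much of this stands: their VRI hospitalisations and deaths are compared by arm in the efficacy tables. On the planning rates the excluded illnesses would also fall mostly on placebo (40 against 8), so leaving them out does not flatter NTZ. But no such rule for serious endpoint events is written in either document, 10.2 asks for deaths from any cause, and the defence fails for subjects whom the efficacy tables omit. If the opposite reading is taken and 10.1 and 10.2 prevail, the hospitalisations reach Table 14.3.1.5 and the gap largely closes. That is why the text has to say which applies.

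It is also fair that the data are not lost. Visits include "Review and recording of adverse events/side effects and complications" (Protocol 5.5), and Listing 16.2.6.2 covers the safety population. This lowers the cost of the fix but does not supply a comparison.

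Three stronger readings are tempting, and the documents do not support them.

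- A reader might infer that headache, fatigue and myalgia are dropped outright, and multiply the 2.7% headache rate in Protocol 1.2.3 by 400 to get 10.8 omitted subjects. The exclusion covers them only as symptoms of a VRI, which 8.3 ties to RT-PCR. A headache without a VRI remains an adverse event. The 2.7% is 2 of 75 subjects treated for 5 days in influenza and cold trials, counted regardless of causality and with rates not significantly different from placebo.
- A reader might infer that no hospitalisation of a baseline-positive subject is compared by arm. Those for non-VRI causes are serious adverse events and enter Table 14.3.1.5.
- A reader might infer that harm in these subjects could show only in deaths. The listing and the safety-population laboratory and vital sign tables also cover them.

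A baseline-positive rate of 10% to 20% would likewise lack support: it would equal or exceed the planned 6-week placebo VRI rate of 10%.

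**Conclusion.** The point holds in a limited form. Protocol 10 conflicts with 10.1 and 10.2 on serious VRI complications, and the passages must be reconciled. The loss of a by-arm comparison is confined to VRI-related, non-fatal hospitalisations in subjects with a virus detected at baseline, and it arises only if Section 10 is the rule that sites follow. At an assumed baseline-positive rate of 1% to 10%, the group is 8 to 80 of 800 subjects; the gap exists at any rate above zero. The IDMC charter and the Medical Monitoring Plan are not among the documents and may contain handling rules that would soften the monitoring part. The missing link between the symptom list and 8.3 is a smaller matter of wording: it leaves room for a blanket exclusion but does not impose one.

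**What to change.** 1. Reconcile Protocol 10 with 10.1 and 10.2 by stating that an event meeting the serious criteria is reported as an SAE even when it is a complication of a VRI.
2. In SAP 5.2 and 8.0, add a table of hospitalisation by arm in the safety population, all-cause and VRI- or COVID-19-related, with baseline virus-positive subjects shown separately.
3. In Protocol 10, refer to the VRI definition in 8.3 for the symptom exclusion. Because that definition ends with the 6-week treatment period, say also how symptoms between Week 6 and Week 8 are recorded.

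The cost is wording in both documents, some more SAE entries, and one table from data already collected for Listing 16.2.6.2. Sample size, visits and the primary analyses do not change.
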